## Clinical Investigation Plan

### COMPLIANCE STATEMENT:

This clinical study will be conducted in accordance with this Clinical Investigation Plan, the Declaration of Helsinki and the applicable regulatory requirements (such as, 21 CFR Part 50, 21 CFR Part 56, 21 CFR Part 812, 21 CFR Part 54, and 21 CFR Part 11 and 45 CFR part 46). The conduct of the clinical study will be approved by the appropriate Institutional Review Board (IRB) of the respective investigational site.

## Clinical Investigation Plan

### 1.0 INTRODUCTION

This document is a clinical investigation plan (CIP) for the clinical study of the Electrode Screening Mode tool, hereafter referred to as the Informity™ tool, on Abbott's Clinician Programmer for the Infinity™ deep brain stimulation (DBS) system. This clinical study is intended to characterize the clinical performance of the Informity tool in programming Infinity DBS systems in patients with Parkinson's disease (PD) or essential tremor (ET). This clinical study is sponsored by Abbott.

This clinical study will be conducted in accordance with this CIP. All investigators involved in the conduct of the clinical study will be qualified by education, training, or experience to perform their tasks and this training will be documented appropriately.

### 1.1 Background and Rationale

#### 1.1.1 Background

Deep brain stimulation (DBS) has become an indispensable therapeutic tool for treating Parkinson's disease, essential tremor, and dystonia, and provides significant symptom relief and quality of life improvement with minimal risk [1]. It is preferred over other surgical treatments due to its adjustability, reversibility, durability, and robust clinical effectiveness and safety.

DBS modulates dysfunctional circuits in the brain so that the brain can function more effectively. This is accomplished by sending continuous electrical signals to specific target areas of the brain, which overrides neural activity that causes neurological dysfunctions. These targets include the subthalamic nucleus (STN), globus pallidus interna (GPi), and ventral intermediate (Vim) nucleus of the thalamus.

[figure not shown]
Patients with DBS experience considerable improvements in their motor symptoms and are able to greatly reduce their medications [2-4]. DBS allows for both unilateral and bilateral coverage of symptoms, can be tailored to a patient's clinical status by adjusting stimulation parameters, and can provide continuous symptom control 24 hours a day with minimum patient and clinician involvement. The electrodes and electrical systems that provide stimulation are generally very well tolerated with no significant changes in surrounding brain tissue [5].

Despite the proven efficacy of DBS, the benefit of this therapy is highly dependent on the location of the DBS lead and the distribution of the stimulation field within the brain anatomy. DBS requires millimeter accuracy in targeting of specific deep brain nuclei, and precise control over the volume of tissue activated (VTA) via programming of stimulation parameters. When the lead is misplaced or the system is incorrectly programmed, this may cause electrical current to spread to the surrounding associative, motor and limbic areas running near the target nuclei, which can lead to side effects. Common side effects include cognitive impairment, memory deficits, difficulties with speech, disequilibrium, dysphagia, and motor and sensory disturbances [6].

[figure not shown]
Conventional DBS leads use omnidirectional electrodes that disperse current axially and symmetrically around the activated contacts. Given the radial dispersion of current, a high level of precision is necessary in lead placement to ensure effective therapy [7, 8]. Clinical studies have indicated that accurate placement of DBS leads is correlated to clinical efficacy [9, 10]. Further, limitations in the omnidirectional electrode design translate to restrictions in the ability to sculpt the shape and size of the VTA, resulting in inadequate activated tissue volumes or inaccurate targeting of therapeutic regions [9, 11, 12].

## Clinical Investigation Plan

Recently, the development of directional DBS leads with segmented electrodes allows for focal current steering and improved clinical effectiveness [7, 11, 13, 14]. Computational modeling studies have shown that segmentation of the electrodes allows for expanded programming options, which could potentially reduce side effects, widen the therapeutic range, and lower the therapeutic current [12, 13, 15]. By using segmented electrodes to control the shape of the VTA, the delivered stimulation field better fits the anatomy of the therapeutic target (Figure 1). Based on a computational model developed by Keane et al, smaller directionally segmented electrodes demonstrated superior targeting of the cerebello-thalamo-cortical pathway, especially in cases of misaligned DBS leads [7]. Modelling also suggests that segmentation of the electrode allows for an increase in magnitude of the activating function and electrode impedance while lowering the required stimulation intensity; thus, creating a greater radial distance of the VTA when compared to standard electrodes [13, 14]. The targeted areas within anatomical structures (STN, GPi, and Vim thalamus) have restricted sizes that are associated with effective treatment. Figure 2 depicts a relative illustration of the DBS targets and the target areas within anatomic structures associated with effective treatment. Shaping the VTA with respect to the position of the electrode segment and target structure allows for improved therapeutic outcomes.

**Figure 1:** Finite element model comparison of (A) omnidirectional stimulation versus (B) unidirectional stimulation using segmented electrodes.

**Figure 2:** DBS targets [8]

[figure not shown]
## Clinical Investigation Plan

The 8 channel Infinity DBS system incorporates this concept of segmentation and directionality. This system includes directional leads, extensions, implanted pulse generators, clinician programmers, and patient controllers. Numerous publications with similar DBS systems and the market experience associated with the currently marketed Infinity DBS system demonstrate the safety and performance of the 8 channel directional DBS leads, extensions and related accessories for treatment of movement disorders.

[figure not shown]
The efficacy of directional DBS (dDBS) for the treatment of patients with movement disorders is supported with data from three prospective clinical studies. Pollo et al (2014) conducted a prospective, single-center acute study to assess the effectiveness of dDBS in PD and tremor patients [9]. Compared to omnidirectional mode, directional stimulation in the best direction had a therapeutic window (current difference between side effects and therapeutic benefit) that was 41.3% wider than omnidirectional stimulation, and a therapeutic amplitude that was 43% lower than omnidirectional stimulation. Having a wider therapeutic window allows for expanded programming options, especially in cases of lead migration or brain shift, without a need for surgical intervention to regain therapeutic benefit. No adverse events were observed during the implantation of and stimulation using the dDBS lead. An acute evaluation of a dDBS lead was also conducted by Contarino et al (2014) [16]. Directional stimulation proved effective in this study in that it reduced the appearance of side effects, while widening the therapeutic window by redirecting the field of stimulation away from the anatomical structures responsible for the unwanted stimulation effects. No unexpected adverse events were observed during the implantation of and stimulation using the dDBS lead. Finally, Steigerwald et al (2016) performed an assessment of dDBS leads in Parkinson's disease patients, and found that directional current steering increased the therapeutic window size compared to omnidirectional stimulation, although in a highly patient-specific manner [17]. No unexpected adverse events were reported with the use of the dDBS lead.

The full benefits of dDBS are only realized if the stimulation parameters are selected appropriately to focus the VTA within the targeted brain area and avoid non-targeted brain regions. The Infirmity tool, available within the Clinician Programmer iPad application (Artemis version 3.7 or later), provides a standardized workflow to guide clinicians or trained healthcare providers through the DBS monopolar review screening process. This process involves assessment of the stimulation amplitudes that produce partial or complete therapeutic benefits and transient or sustained side effects, and is performed by individually testing each of the different electrodes on the dDBS lead. The Infirmity tool enables the neurologist to simultaneously perform this testing on a patient and record the results (Figure 3). Moreover, the tool allows the neurologist to review the results in different formats to aid in the selection of the best contact configuration for that patient (Figure 4). The selection of the best contact configuration is made on the basis of maximizing the width of the therapeutic window and minimizing stimulation power (total electrical energy delivered [TEED]).

## Clinical Investigation Plan

**Figure 3:** Interface of the Informity tool during the monopolar review screening process.

**Figure 4:** Interface of the Informity tool showing the results of the monopolar review screening process in a graphical view (left) and a comparison table view (right).

### 1.1.2 Rationale for Conducting this Clinical Study

The purpose of this post-market clinical study is to characterize the clinical performance of the Informity tool in programming Infinity DBS systems in patients with PD or ET.

## Clinical Investigation Plan

### 2.0 CLINICAL STUDY OVERVIEW

#### 2.1 Clinical Study Objective

##### 2.1.1 Primary objective

The objective of this clinical study is to characterize the clinical performance of the Infirmity tool in programming the Infinity DBS system for treatment of Parkinson's disease and essential tremor.

#### 2.2 Device(s) To Be Used in the Clinical Study

##### 2.2.1 Name of the Device(s) Under Investigation

Device name	Model/ Type	Serial/Lot Controlled	Manufacturer	Region/ Country	Investigational or Market Released	MRI Status
Infinity IPG	6660, 6662	Serial Controlled	St. Jude Medical*	USA	Market Released	MR Conditional
Directional Lead for the Infinity DBS System	6170, 6171, 6172, 6173	Lot Controlled	St. Jude Medical*	USA	Market Released	MR Conditional
Infinity DBS System 8 Channel Flex Extension	6371, 6372, 6373	Lot Controlled	St. Jude Medical*	USA	Market Released	MR Conditional: 6371, 6372 MR Unsafe: 6373
Clinician Programmer App (Artemis™ version 3.7 or later)	3874	Serial Controlled	St. Jude Medical*	USA	Market Released	Not applicable
Patient Controller App	3875	Serial Controlled	St. Jude Medical*	USA	Market Released	Not applicable

\* St. Jude Medical is an Abbott company

This post-market study is investigating the Infirmity tool on the Clinician Programmer App (Artemis version 3.7 or later), which is illustrated in Figures 3 and 4 of Section 1.1.1. Further details about the Clinician Programmer App are provided in the Instructions for Use (IFU).

##### 2.2.2 Indications for Use

The indications for use of the Clinician Programmer App (Artemis version 3.7 or later) and other devices to be used in this study are bilateral stimulation of the subthalamic nucleus (STN) as an adjunctive

*This confidential document is the property of Abbott and shall not be reproduced, distributed, disclosed or used without the express written consent of Abbott*

## Clinical Investigation Plan

therapy to reduce some of the symptoms of advanced levodopa-responsive Parkinson's disease that are not adequately controlled by medications, and unilateral or bilateral stimulation of the ventral intermediate nucleus (VIM) of the thalamus for the suppression of disabling upper extremity tremor in adult essential tremor patients whose tremor is not adequately controlled by medications and where the tremor constitutes a significant functional disability.

### 2.2.3 Description of the Device(s) Under Investigation

Please refer to the respective IFU for the list of anticipated adverse effects and additional information regarding the device used in this clinical study.

## 3.0 CLINICAL STUDY DESIGN

This is a prospective, non-randomized, single-arm, multi-center, post-market clinical study designed to evaluate Abbott's Informity tool for Infinity DBS systems.

This clinical study will be conducted at up to 5 centers in the United States.

[figure not shown]
Up to 40 patients will be enrolled in the study. Of these subjects, up to 20 will have PD and up to 20 will have ET. All patients will have received DBS systems prior to enrolling in the study.

The primary and secondary endpoints will be evaluated when all subjects have completed their 6-month follow-up visit.

### 3.1 Clinical Study Procedures and Follow-up Schedule

The flow chart and the follow-up requirements of this clinical study are described below.

## Clinical Investigation Plan

**Figure 5:** Clinical Study Flow Chart

Patients who currently have an Infinity DBS system and meet the standard requirements will be approached to participate in the study. The patient will be informed about the study to determine if he/she is interested in participating. If the patient provides informed consent, then he/she will be screened according to the inclusion/exclusion criteria. If the patient meets the study inclusion criteria and none of the exclusion criteria, he/she is enrolled in the study and becomes a study subject.

At the baseline visit following enrollment, information will be collected on subject demographics and disease history, baseline programming parameters, medication, preoperative motor symptom and quality of life assessments, and DBS implant details. A motor symptom evaluation and quality of life assessment will also be performed at baseline. Subsequently, subjects will undergo Informity programming with the Informity tool, and programming details, programmer experience and programmer satisfaction will be recorded. Follow-up visits will be conducted at 3 and 6 months after the Informity programming visit, for collection of medication information, motor symptom evaluation and quality of life assessment, and recording of programming details. In addition, the subjects will be assessed for any adverse events that should be documented and submitted to the Sponsor.

*This confidential document is the property of Abbott and shall not be reproduced, distributed, disclosed or used without the express written consent of Abbott*

## Clinical Investigation Plan

### 3.2 Measures Taken to Avoid and Minimize Bias

There are several measures that will be taken in this study to minimize bias. First, the person who uses the Informity tool to program a patient in the study must be different from the person who programmed the settings used at baseline. Second, the motor symptom evaluation will be evaluated by a blinded assessor.

Since this study design is open-label and non-controlled, there is a possibility of bias from placebo response following programming with the Informity tool.

### 3.3 Suspension or Early Termination of the Clinical Study

No formal statistical rule for early termination of the clinical study for insufficient effectiveness of the device under investigation is defined.

The Sponsor reserves the right to discontinue the clinical study at any stage or reduce the follow-up period with suitable written notice to the investigator.

Should the clinical study be discontinued by the Sponsor, subjects will be followed per routine hospital practice with device-related AEs reported to the Sponsor as per commercial reporting requirements. No additional subject follow-ups will be required following an early termination or suspension.

Should this occur, the investigator shall return all clinical study materials to the Sponsor, and provide a written statement as to why the premature termination has taken place to the IRB (if applicable). All applicable clinical study documents shall be subject to the same retention policy as detailed in Section 11.5 of the CIP.

A Principal Investigator, IRB or regulatory authority may suspend or prematurely terminate participation in a clinical study at the investigational sites for which they are responsible. The investigators will follow the requirements specified in the Clinical Trial Agreement.

If the Sponsor suspends or prematurely terminates the clinical study at an individual site in the interest of safety, the Sponsor will inform all other Principal Investigators.

If suspension or premature termination occurs, the Sponsor will remain responsible for providing resources to fulfill the obligations from the CIP and existing agreements for following the subjects enrolled in the clinical study, and the Principal Investigator or authorized designee will promptly inform the enrolled subjects at his/her site, if appropriate.

## 4.0 ENDPOINTS

### 4.1 Primary Endpoints and Rationale

- 1) Change in therapeutic window size at the Informity programming visit compared to baseline
- 2) Change in TEED at the Informity programming visit compared to baseline

The primary endpoints were selected because it is hypothesized that they will be significantly improved following Infinity tool programming. Specifically, it is hypothesized that therapeutic window size will increase and TEED will decrease at the Informity programming visit compared to baseline.

*This confidential document is the property of Abbott and shall not be reproduced, distributed, disclosed or used without the express written consent of Abbott*

## Clinical Investigation Plan

### 4.2 Secondary Endpoints

- 1) Change in UPDRS III for PD subjects or Fahn-Tolosa-Marin tremor rating scale for ET subjects at 3- and 6-month follow-up visits compared to baseline
- 2) Change in quality of life measurement as measured by the PDQ-39 for PD subjects or QUEST for ET subjects at the 3- and 6-month follow-up visits compared to baseline
- 3) Duration of programming at the Informity programming visit compared to the most recent programming session prior to enrollment
- 4) Change in TEED at the 3- and 6-month follow-up visits compared to baseline

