### 5.2 Subject Screening and Informed Consent

#### 5.2.1 Subject Screening

Potential patients presenting at the clinical sites will be fully informed about the clinical study, following the established Informed Consent process (described in Section 5.2.2). Once a duly dated and signed Informed Consent form is obtained, the clinical study-specific screening procedures may begin.

The following assessments are performed as part of the screening process:

- Review of patient's medical records
- Review of patient's Infinity DBS system using the Clinician Programmer
- Interview with the patient

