#### 5.3.2 Inclusion Criteria

##### 5.3.2.1 General Inclusion Criteria

###### 5.3.2.1.1 Parkinson's disease patients

1. Patient must provide written informed consent prior to any clinical study related procedure.
2. Patient is 18 to 80 years of age.
3. Patient is diagnosed with Parkinson's disease for at least 4 years according to standard practice.
4. Patient is willing to maintain a constant dose of anti-Parkinson's disease medication indicated as best medical management for at least 1 month prior to study enrollment.
5. Patient is willing and able to comply with the follow-up schedule for the length of the study.
6. Patient has been implanted with an 8-channel directional Infinity deep brain stimulation system in the subthalamic nucleus (STN) within the last 12 months.
7. Patient has had stable deep brain stimulation programming settings for at least 1 month prior to study enrollment.

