### 5.4 Subject Enrollment

A patient is considered enrolled in the clinical study from the moment the patient provides written informed consent and has been confirmed to meet all inclusion criteria and none of the exclusion criteria. Omnidirectional programming should be used from the time of enrollment to the Baseline visit.

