## Clinical Investigation Plan

### 6.0 TREATMENT AND EVALUATION OF ENDPOINTS

#### 6.1 Baseline

##### 6.1.1 Baseline Assessments

Subjects should have omnidirectional stimulation in use at the time of the Baseline visit. Informity should not be used. The following assessments and information will be collected at the Baseline visit:

- Demographics- subject's age and gender
- Disease history- subject's year of PD or ET symptom onset, year of initial PD or ET diagnosis, subject's impression of worst symptom (PD subjects only)
- Baseline programming- subject's current DBS programming parameters
- Therapeutic window of current parameter set
- TEED of current parameter set
- Duration of the most recent programming session preceding enrollment from the Clinician Programmer session logs (if available)
- Medication dosage (only PD or ET medications)- indicate the drug category the subject is currently taking on a long term basis, i.e. no short term medication
- Preoperative motor symptom evaluation (medication ON) from medical records (if available)
- Preoperative quality of life assessment from medical records (if available)
- DBS implant information
- Pre-op MRI and post-op CT images

An encrypted thumb drive containing de-identified MRI and CT images for all study subjects will be provided to sites and images will be sent to the Sponsor.

The following activities will be performed at the Baseline visit:

- Quality of life assessment
- Motor symptom evaluation (stimulation ON/medication ON) performed by a blinded assessor

The quality of life assessment must be performed prior to the motor symptom evaluation. Quality of life assessments will be performed using PDQ-39 for PD subjects, and QUEST for ET subjects (see Section 6.3.2). Quality of life assessment does not need to be collected if a patient was reprogrammed to omnidirectional stimulation on the same day as the Baseline visit. Motor symptom evaluation will be performed using UPDRS part III for PD subjects and Fahn-Tolosa-Marin tremor rating scale for ET subjects. For both evaluations, responses are rated on a 0 to 4-point scale where 0 indicates 'none' and 4 indicates 'severe' symptom. Motor symptom evaluation will be performed by a blinded assessor, who will not be aware of the subject's programming.

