#### 8.1.2 Secondary Effectiveness Endpoint Analyses

The hypotheses for the secondary endpoints are:

1. The Informity tool will identify DBS parameters that improve motor symptom scores compared to baseline
2. The Informity tool will identify DBS parameters that improve quality of life measurements compared to baseline.

The time required for programming with the Informity tool is shorter than that of the most recent programming session prior to enrollment.

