## Clinical Investigation Plan

For the change in motor symptom scores, a repeated measure analysis of variance (RMANOVA) will be conducted to determine statistical differences from baseline. Post-hoc Tukey's pairwise comparisons will follow to determine specific differences between follow-up visits. The change in quality of life measurement will also be analyzed using a RMANOVA followed by Tukey's pairwise comparisons. A comparison of the duration of programming will be performed for the programming session preceding enrollment, and the Informity programming session with the Informity tool, using a paired t-test. All statistical analyses will be conducted assuming a type-1 error rate of 0.05 unless specifically stated otherwise.

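### Secondary endpoint 3 compares a tool session of prescribed scope with a last pre-enrollment session of unrecorded scope, so the time difference mixes the tool's effect with session content.

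*Combined protocol and SAP*

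**What the plan says.** The endpoint in Section 4.2, item 3, is "Duration of programming at the Informity programming visit compared to the most recent programming session prior to enrollment". Section 8.1.2 states the hypothesis: "The time required for programming with the Informity tool is shorter than that of the most recent programming session prior to enrollment". The analysis follows in the same section: "A comparison of the duration of programming will be performed for the programming session preceding enrollment" and for the tool session, by paired t-test at a type-1 error rate of 0.05.

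For the comparator, Section 6.1.1 lists one item: "Duration of the most recent programming session preceding enrollment from the Clinician Programmer session logs (if available". The other baseline programming items describe the settings in use, not what was done when they were chosen.

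The tool session is defined closely. Section 1.1.1 says that the tool "provides a standardized workflow to guide clinicians or trained healthcare providers through the DBS monopolar review screening process". Section 6.2.1 requires several configurations to be assessed on each lead, the best segmented level to be found, and at least its three single segments to be tested, for benefit and then for side effects. It suggests a rest of at least 2 minutes between contacts. With bilateral leads, the work may be split over two consecutive days.

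**The concern.** A paired test removes differences between patients. It does not remove differences in what was done at the two sessions. If the last session before enrollment was a short adjustment, or dealt with one lead only, a full review with the tool will take longer even if the tool saves time on every contact. If that session was long, for example an initial contact screening with troubleshooting, the tool will look faster even if it saves nothing.

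Because the hypothesis is directional and worded as a property of the tool, a significant result either way would probably be read as evidence about the tool. At stake is the interpretation of this one secondary endpoint. The primary endpoints, therapeutic window and TEED at the Informity programming visit, do not use session duration.

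**Working it through.** **Does any section control for scope?**

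- Section 3.2 (bias): a different programmer and a blinded motor assessor. Neither concerns session content.
- Section 5.3.2 (eligibility): "Patient has had stable deep brain stimulation programming settings for at least 1 month prior to study enrollment", with the same criterion for essential tremor, and an implant within the last 12 months. This limits when settings last changed, not what kind of session changed them.
- Section 8.3 (subgroups): diagnosis, and baseline use of contact 2 or 3. Neither is session scope.
- Section 8.5 (missing data): excludes subjects whose session log is missing or corrupted, and no others.
- Section 2.2.2 (indications): stimulation for essential tremor may be unilateral or bilateral, so lead coverage can vary between subjects. In a bilateral subject, the last session may have covered one side.

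None restricts or adjusts for the comparator's type or leads.

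**How lead coverage alone adds time.** If the suggested rest is followed, testing three segments on one lead includes 2 x (3 - 1) = 4 minutes of rest. Two leads, counted separately, include 8 minutes. This comes before any time spent finding the best segmented level.

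**Size, for illustration.** The plan gives no duration, SD, power or session mix for this endpoint, so there is no figure to reproduce. All inputs below are assumptions except n = 40, the maximum enrollment (Section 5.8), which presumes a usable log for everyone.

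- f: share of comparators shorter than a like-for-like session (25, 50, 75%)
- d: how much shorter (15 or 30 minutes)
- SD: paired SD without the mixture (20, 30, 40 minutes)
- true tool effect: 0
- test: two-sided at 0.05 (the plan does not state sidedness)

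Mean shift = f x d. SD with mixture = sqrt(SD² + f(1 - f)d²). The chance of a significant "slower" result is the upper tail of a noncentral t with 39 degrees of freedom and noncentrality sqrt(40) x shift / SD with mixture.

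Example: f = 50%, d = 15, SD = 30. Shift = 7.5 minutes. SD with mixture = sqrt(900 + 0.25 x 225) = 30.92. Noncentrality = 6.325 x 7.5 / 30.92 = 1.53. Probability = 0.32.

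| f | Shift, d = 15 | Probability at SD 20/30/40 | Shift, d = 30 | Probability at SD 20/30/40 |
|---|---|---|---|---|
| 25% | 3.75 min | 0.20/0.11/0.08 | 7.5 min | 0.49/0.29/0.20 |
| 50% | 7.5 min | 0.58/0.32/0.21 | 15 min | 0.96/0.79/0.58 |
| 75% | 11.25 min | 0.91/0.62/0.40 | 22.5 min | 1.00/0.99/0.91 |

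With no mixture, each entry would be 0.025. A simulation of the two-type mixture agrees to within about 0.005. The table is symmetric: if the comparators were longer by d instead, the same values are the chance of a false "shorter" result.

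**Precision of a restricted comparison.** The difference detectable with 80% power is 0.454 SD at 40 pairs and 0.660 SD at 20 pairs. At SD 20/30/40 minutes that is 9/14/18 minutes against 13/20/26 minutes.

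**The case against.** The strongest reply has four parts.

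**The comparator is clear enough.** The endpoint refers to a programming session. Together with the stable-settings criterion, this most naturally means the session that last set the patient's settings. A reader might infer that the eligibility check of the "Infinity DBS system using the Clinician Programmer" (Section 5.2.1) could count as the most recent session, because it comes before enrollment is complete: "A patient is considered enrolled in the clinical study from the moment the patient provides written informed consent and has been confirmed". The documents do not support that inference. The check is called a review, and Section 6.3.1 treats interrogating settings and re-programming as separate acts. This part of the reply stands. It does not settle the scope question, because the session that last set the settings could still be a full screening or a small change on one lead.

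**Split days.** A reader might infer that only one day would be counted, which would halve the recorded tool time if the days were equal. Section 6.2.1 describes one procedure that can be divided, so the total is the natural reading. Section 6.2.2 gives no summing rule, so one sentence is worth adding, but this is not evidence of bias.

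**The magnitude is assumed.** This stands in full. The result depends almost entirely on f and d, and no section describes the session mix.

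**The setting is modest.** This is one secondary endpoint in a single-arm post-market study meant to characterize performance. Section 8.0 allows a separate SAP, and the case report forms are under separate cover (Appendix V), so session type may be captured there. That lowers confidence. But the endpoint, hypothesis and test are set in the CIP, and none uses session scope.

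**Conclusion.** The point holds. As written, the comparison cannot separate a time saving due to the tool from a difference in what the two sessions covered. Neither the direction nor the size can be determined from the documents. Under the assumptions shown, with 40 pairs and no tool effect, the chance of a false directional result is about 0.08 to 0.49 at f = 25%, 0.21 to 0.96 at f = 50% and 0.40 to 1.00 at f = 75%. These figures show that scope could decide the result, not that it will.

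A reader might go further and infer that the design favors the tool. The documents do not support that, since short comparators would work against the sponsor's hypothesis. Nor do they support discarding the all-comer comparison: the last real-world session is a legitimate descriptive reference. What fails is attributing the difference to the tool. The point merits a change because the remedy is cheap and alters what the endpoint can conclude. Confidence is medium, because the case report forms and any separate SAP were not available.

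**What to change.** Amend Sections 4.2 (item 3), 6.1.1 and 8.1.2:

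1. Record the comparator session's type (contact screening or monopolar review, versus adjustment or check) and the lead or leads covered. Take these from the session log or the medical records already reviewed at screening, and classify them without reference to the durations.
2. Define tool time as the sum over both days when programming is split.
3. Keep the all-comer comparison, but report it by session type and lead coverage. Add a prespecified comparison limited to like-scope sessions on the same lead or leads. Draw any conclusion that programming is shorter with the tool only from that comparison. Report the endpoint descriptively if there are fewer like-scope pairs than a minimum fixed in advance.
4. State as limitations the different programmer (Sections 3.2 and 6.2.1) and the off-medication state of the tool session (Section 6.2.1). The comparator's medication state is not specified.

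A sentence saying that the screening review is not the comparator is optional.

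The cost is two data items, a log or chart check per subject, and wording in three sections. No section shows that the logs identify session type, so charts may be needed. The like-scope comparison will have fewer pairs and less precision, and may end up descriptive. The different programmer and the medication state will still limit attribution.
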